#### **6.6.3.3 Treatment of Nivolumab and Ipilimumab-Related Infusion Reactions**

Since nivolumab and ipilimumab contain only human immunoglobulin protein sequences, it is unlikely to be immunogenic and induce infusion or hypersensitivity reactions. However, if such a reaction were to occur, it might manifest with fever, chills, rigors, headache, rash, pruritus, arthralgias, hypotension, hypertension, bronchospasm, or other allergic-like reactions.

CONFIDENTIAL

Regardless of whether the event is attributed to these study drugs, all Grade 3 or 4 infusion reactions should be reported within 24 hours to the study Sponsor Medical Monitor or designee and reported as an SAE if it meets the criteria. Infusion reactions should be graded according to CTCAE v5 guidelines.

Treatment recommendations are provided below and may be modified based on local treatment standards and guidelines, as appropriate:

For Grade 1 symptoms: (mild reaction; infusion interruption not indicated; intervention not indicated):

Remain at bedside and monitor participant until recovery from symptoms. The following prophylactic premedications are recommended for future infusions: diphenhydramine 50 mg (or equivalent) and/or acetaminophen/paracetamol 325 to 1000 mg at least 30 minutes before additional administrations of these study drugs.

For Grade 2 symptoms: (moderate reaction; required therapy or infusion interruption but responds promptly to symptomatic treatment [eg, antihistamines, non-steroidal anti-inflammatory drugs, narcotics, corticosteroids, bronchodilators, IV fluids]; prophylactic medications indicated for  $\leq$  24 hours):

Stop the study drug infusion, begin an IV infusion of normal saline, and treat the participant with diphenhydramine 50 mg IV (or equivalent) and/or acetaminophen/paracetamol 325 to 1000 mg; remain at bedside and monitor participant until resolution of symptoms. Corticosteroid and/or bronchodilator therapy may also be administered as appropriate. If the infusion is interrupted, then restart the infusion at 50% of the original infusion rate when symptoms resolve; if no further complications ensue after 30 minutes, the rate may be increased to 100% of the original infusion rate. Monitor participant closely. If symptoms recur, then no further study drug will be administered at that visit.

For future infusions, the following prophylactic premedications are recommended: diphenhydramine 50 mg (or equivalent) and/or acetaminophen/paracetamol 325 to 1000 mg should be administered at least 30 minutes before study drug infusions. If necessary, corticosteroids (up to 25 mg of hydrocortisone or equivalent) may be used.

For Grade 3 or 4 symptoms: (severe reaction; Grade 3: prolonged [ie, not rapidly responsive to symptomatic medication and/or brief interruption of infusion]; recurrence of symptoms following initial improvement; hospitalization indicated for other clinical sequelae (eg, renal

CONFIDENTIAL

Protocol XL184-313 Protocol Amendment 3.0  
Page 110 of 193

impairment, pulmonary infiltrates). Grade 4: Life-threatening; pressor or ventilatory support indicated):

Immediately discontinue infusion of these study drugs. Begin an IV infusion of normal saline and treat the participant as follows: Recommend bronchodilators, epinephrine 0.2 to 1 mg of a 1:1000 solution for subcutaneous administration or 0.1 to 0.25 mg of a 1:10,000 solution injected slowly for IV administration, and/or diphenhydramine 50 mg IV with methylprednisolone 100 mg IV (or equivalent), as needed. Participant should be monitored until the Investigator is comfortable that the symptoms will not recur. Nivolumab + ipilimumab will be permanently discontinued. Investigators should follow their institutional guidelines for the treatment of anaphylaxis. Remain at bedside and monitor participant until recovery of the symptoms.

In case of late-occurring hypersensitivity symptoms (eg, appearance of a localized or generalized pruritus within 1 week after treatment), symptomatic treatment may be given (eg, oral antihistamine or corticosteroids).

## **7 CONCOMITANT MEDICATIONS AND THERAPIES**

### **7.1 Allowed Therapy**

- Antiemetics and antidiarrheal medications are allowed prophylactically according to standard clinical practice if clinically indicated.
- Adrenal replacement steroid doses at > 10 mg daily prednisone equivalent are permitted.
- Granulocyte colony-stimulating factors (G-CSF or GM-CSF) are allowed if used per clinical guidelines (eg, ASCO or ESMO guidelines).
- Bisphosphonates or RANK-L inhibitors can be used per standard of care if the benefit outweighs the risk per the Investigator's discretion

Note: osteonecrosis of the jaw (ONJ) has been reported in subjects using bisphosphonates. Oral examinations are recommended at screening to determine eligibility and periodically during the study. In addition, subjects should be advised regarding oral hygiene practice and to quickly report symptoms to the Investigator. Frequent monitoring for potentially overlapping toxicities with study treatment is recommended.

- Transfusions and hormone replacement should be utilized as indicated by standard clinical practice.

CONFIDENTIAL

Protocol XL184-313 Protocol Amendment 3.0  
Page 111 of 193

- Inhaled, intranasal, intra-articular, and topical corticosteroids are allowed if minimal systemic absorption. Systemic corticosteroids are allowed for control of infusion reactions or irAEs and must be tapered to a dose level  $\leq 10$  mg/day of prednisone equivalent before next nivolumab/ipilimumab administration. Prophylactic steroid treatment for subjects with contrast allergies prior to tumor imaging is allowed.
- Individualized anticoagulation therapy with heparin is allowed if it can be provided safely and effectively under the following circumstances:
  - *Low dose low molecular weight heparins (LMWH) for prophylactic use* are allowed if clinically indicated and the benefit outweighs the risk per the Investigator's discretion.
  - *Therapeutic doses of LMWH at the time of the first dose of study treatment* are allowed if the subject has no evidence of brain metastasis, has been on a stable dose of LMWH for at least 1 week, and has had no complications from a thromboembolic event or the anticoagulation regimen.
  - *Therapeutic doses of LMWH after first dose of study treatment* are allowed if clinically indicated (eg, for the treatment of DVT), and the benefit outweighs the risk per the Investigator's discretion. For management of thromboembolic complications while on study, refer to [Section 6.6.2.1.4](#).
  - Accepted clinical guidelines regarding appropriate management while receiving anticoagulation therapy with heparins must be followed. This includes, but is not limited to, subject education regarding potential adverse drug reactions, monitoring laboratory parameters, dose adjustments (eg, due to kidney dysfunction).
  - For restrictions on oral anticoagulants see [Section 7.2](#).

Potential drug interactions with cabozantinib are summarized in [Section 7.3.1](#). The drug interaction potential of nivolumab is unknown as no formal PK drug-drug interaction studies have been conducted (nivolumab US prescribing information).

CONFIDENTIAL

Protocol XL184-313 Protocol Amendment 3.0  
Page 112 of 193

## 7.2 Prohibited or Restricted Therapy

The following therapies are prohibited until study treatment has been permanently discontinued:

- Any investigational agent or investigational medical device.
- Oral anticoagulants (eg, warfarin or other coumarin-related agents, direct thrombin or direct FXa inhibitors, or antiplatelet agents such as clopidogrel, or chronic use of aspirin above low dose levels for cardioprotection per local applicable guidelines), unless blinded oral study treatment has been permanently discontinued.
- Any non-protocol systemic anti-cancer treatment (eg, chemotherapy, immunotherapy, radionuclides, drugs specifically for the treatment of the cancer under investigation).
- Immunosuppressive agents including immunosuppressive doses of systemic corticosteroids with exceptions as stated in [Section 7.1](#) except when both nivolumab and ipilimumab have been permanently discontinued.
- Live vaccines are prohibited -during treatment and until 100 days after the last doses of nivolumab and ipilimumab (eg, intranasal influenza, measles, mumps, rubella, oral polio, BCG, yellow fever, varicella, and TY21a typhoid vaccines).
- The use of inactivated (killed) vaccines for the prevention of infectious disease is permitted.

*The following therapies should be avoided until study treatment has been permanently discontinued or until otherwise specified:*

- Local anti-cancer treatment including palliative radiation, ablation, embolization, or surgery with impact on tumor lesions should not be performed until radiographic progression per RECIST 1.1 has been established. If clinically unavoidable, the Investigator should consult the Sponsor prior to the procedure for safety guidance.
- Erythropoietic stimulating agents (eg, epoetin alfa and darbepoetin alfa) should not be used based on a report of increased risk of tumor recurrence/progression associated with erythropoietin (Wright et al 2007).
- Concomitant medications known to prolong the QTc interval should be avoided in subjects who receive cabozantinib until they have permanently discontinued cabozantinib treatment

(refer to <http://www.qtdrugs.org> for a list of drugs which have the potential to prolong the QTc interval).

- Chronic co-administration of cabozantinib with strong inducers of the CYP3A4 family (eg, phenytoin, carbamazepine, rifampin, rifabutin, rifapentine, phenobarbital, and St. John's Wort) may significantly decrease cabozantinib concentrations and should be avoided ([Appendix G](#)). Selection of alternate concomitant medications with no or minimal CYP3A4 enzyme induction potential is recommended.
- Caution must be used when discontinuing treatment with a strong CYP3A4 inducer in a subject who has been concurrently receiving a stable dose of cabozantinib, as this could significantly increase the exposure to cabozantinib.
- Co-administration of cabozantinib with strong inhibitors of the CYP3A4 family (eg, boceprevir, conivaptan, posaconazole, ketoconazole, itraconazole, clarithromycin, atazanavir, indinavir, nefazodone, neflifavir, saquinavir, ritonavir, lopinavir, telaprevir, telithromycin, and voriconazole) may increase cabozantinib concentrations and should be avoided ([Appendix G](#)). Grapefruit, star fruit, and Seville oranges may also increase plasma concentrations of cabozantinib and should be avoided.

Additional information on potential drug interactions with cabozantinib is provided in [Section 7.3.1](#).

The US prescribing information for nivolumab and ipilimumab notes that no formal PK drug-drug interaction studies have been conducted using these agents.

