AST or ALT > 5 x ULN or total bili > 3 x ULN, regardless of baseline value	
 
Cabozantinib: 
 
Discontinue cabozantinib if ALT or AST > 8 x ULN.
 
Otherwise interrupt cabozantinib dosing and resume at a reduced dose after LFTs return to baseline grade (Sponsor approval required)
 
 
 
Nivolumab /Ipilimumab: 
 
Delay dose or permanently discontinue.
 
 
 
	
 
Monitor LFTs twice weekly or more frequently as deemed clinically necessary.
 
During steroid taper, monitor LFTs once weekly or more often per clinical judgmentc.
 
For AST or ALT > 5 x ULN to <math>\leq</math> 20 x ULN, or total bilirubin > 3 x ULN to <math>\leq</math> 10 x ULN: 
 
Administer 1.0-2.0 mg/kg/day methylprednisolone IV or IV equivalent.
 
 
 
For AST or ALT > 20 x ULN, or total bilirubin > 10 x ULN: 
 
Administer 2.0 mg/kg/day methylprednisolone IV or IV equivalent.
 
 
 

CONFIDENTIAL

Severity of LFT a Elevations by Laboratory Value	Dose Modification Guidance b	Management/Follow-up Guidance
	
* In most cases of AST or ALT <math>> 5 \times</math> ULN, study treatment will be permanently discontinued. If the investigator determines a possible favorable benefit/risk ratio that warrants continuation of study treatment, a discussion between the investigator and the Medical Monitor/ designee must occur and approval from Medical Monitor prior to resuming therapy must be obtained.
	
 
• Add prophylactic antibiotics for opportunistic infections.
 
• Consult Gastroenterologist.
 
• If LFT elevations do not improve in <math>> 3</math> days, worsen or rebound: 
 
– Add mycophenolate mofetil 1g BID.
 
– If no response within an additional 3-5 days, consider other immunosuppressants per local guidelines.
 
 
 
• Dosing may resume when laboratory values return to baseline.
 
• Taper steroids over at least 1 monthc.
 

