## GI Adverse Event Management Algorithm

Rule out non-inflammatory causes. If non-inflammatory cause is identified, treat accordingly and continue I-O therapy.  
Opiates/narcotics may mask symptoms of perforation. Infliximab should not be used in cases of perforation or sepsis.

[figure not shown]
Patients on IV steroids may be switched to an equivalent dose of oral corticosteroids (eg, prednisone) at start of tapering or earlier, after sustained clinical improvement is observed. Lower bioavailability of oral corticosteroids should be taken into account when switching to the equivalent dose of oral corticosteroids.

\* Discontinue for Grade 4 diarrhea or colitis. For Grade 3 diarrhea or colitis, 1) Nivolumab monotherapy: Nivolumab can be delayed. 2) Nivolumab+ Ipilimumab combination: Ipilimumab should be discontinued while nivolumab can be delayed. Nivolumab monotherapy can be resumed when symptoms improve to Grade 1. Please refer to protocol for dose delay and discontinue criteria for other combinations.

CONFIDENTIAL

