# **9.            IDENTIFICATION AND SUMMARY OF PROTOCOL DEVIATIONS**

Important protocol deviations are pre-specified in the study Protocol Deviation Management Plan. In accordance with ICH E3 (1995), important eligibility deviations per the inclusion/exclusion criteria (documented on study CRFs) and important post-randomization protocol deviations (tracked in study clinical trial management system, CTMS) will be identified and listed separately by study center and subject. Important deviations will be summarized for

the ITT population by deviation code (a standardized description e.g. “did not satisfy eligibility criteria” or “received prohibited medication”) and deviation category (a standardized severity classification: “important” or “not important”).

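### Section 7.2 prohibits non-steroid immunosuppressants while an antibody is only delayed, yet Table 6-3 suggests mycophenolate in that same situation

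*Protocol*

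**What the plan says.** **The prohibition.** Protocol Section 7.2 opens its list with "The following therapies are prohibited until study treatment has been permanently discontinued". One entry is "Immunosuppressive agents including immunosuppressive doses of systemic corticosteroids with exceptions as stated in" Section 7.1. That entry has a single release condition: "except when both nivolumab and ipilimumab have been permanently discontinued".

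**The exceptions.** For immune-related events, Section 7.1 states "Systemic corticosteroids are allowed for control of infusion reactions or irAEs and must be tapered to a dose level" of no more than 10 mg/day prednisone equivalent before the next antibody dose. Its other relevant entries cover inhaled, intranasal, intra-articular and topical steroids, adrenal replacement, and steroid prophylaxis for contrast allergy. It names no non-steroid immunosuppressant.

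**The liver guidance.** In the Table 6-3 row for AST/ALT above 5 x ULN or bilirubin above 3 x ULN, nivolumab and ipilimumab may be either delayed or permanently stopped. If liver tests fail to improve in more than 3 days, worsen or rebound, the row says "Add mycophenolate mofetil 1g BID", and then "If no response within an additional 3-5 days, consider other immunosuppressants per local guidelines". The same cell lets dosing resume once laboratory values are back at baseline. A note in the row expects permanent discontinuation in most cases of AST/ALT above 5 x ULN, and requires discussion with and approval from the Medical Monitor before resuming. The table's title calls the management suggested. Section 6.6 says investigators should follow Section 6.6.1, which contains the table.

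**The GI guidance.** The surviving text of the GI algorithm in Appendix E says "Infliximab should not be used in cases of perforation or sepsis".

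**The SAP.** Section 6.4 summarises immune-modulating medications used to manage adverse events. Section 9 gives "received prohibited medication" as an example of a deviation code.

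**The concern.** Second-line immunosuppression comes into play when a liver event is severe and is not settling on steroids. At that moment a site needs one rule. A site that treats Section 7.2 as binding must either withhold the drug that Table 6-3 suggests, or permanently stop both antibodies in order to give it. A site that follows Table 6-3 gives a drug on the prohibited list.

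The choice feeds into what the trial reports. Counts of antibody discontinuation, antibody exposure, use of immune-modulating medication and protocol deviations may all depend on which section the site read. Protocol Section 5.8 also links important or repeated deviations to site re-training, an enrollment hold or site termination, so the classification has consequences for sites as well as for tables.

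**Working it through.** No arithmetic applies. The check is whether one subject can comply with both rules, taken by antibody status within the Table 6-3 row for AST/ALT above 5 x ULN or bilirubin above 3 x ULN, once liver tests have failed to improve, worsened or rebounded.

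| Antibody status | Section 7.2 with 7.1 | Table 6-3 | Can both be followed? |
|---|---|---|---|
| Both permanently stopped | Ban lifted | Mycophenolate step | Yes |
| Both delayed | Ban applies | Mycophenolate step | No |
| One permanently stopped, one delayed | Ban applies, because the release needs both | Mycophenolate step | No |

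1. *Does a delay release the ban?* No. The condition is permanent discontinuation of both antibodies.
2. *Does Section 7.1 rescue mycophenolate?* No. Whether its exceptions are read as qualifying the whole entry or only the corticosteroid clause, every relevant one is a corticosteroid use.
3. *Does Table 6-3 contemplate delay in this row?* Yes. Delay is offered as an alternative to permanent discontinuation, and the cell that contains mycophenolate also provides for resumption.
4. *Which entries to the row are covered by the note on permanent discontinuation?* The note speaks of AST or ALT above 5 x ULN. It does not mention subjects who enter the row on bilirubin alone.
5. *Do other Table 6-3 rows raise the issue?* The row below it in severity goes no further than steroids. The row combining raised ALT/AST and bilirubin without biliary obstruction requires all study drugs to be discontinued, so the Section 7.2 release applies there.
6. *Is there a cross-reference or order of precedence?* None was found. Section 7.2 and Table 6-3 do not refer to each other on this point. The restart criteria in Section 6.6.3.2.1 address steroid taper and are silent on other immunosuppressants. They send the reader to Appendix E for the full list, but its algorithm figures are not shown in the text reviewed.
7. *Does the gap extend to GI events?* Probably. For Grade 3 colitis or diarrhea on the combination, Table 6-10 and the GI algorithm footnote stop ipilimumab but let nivolumab be delayed and resumed, so the release condition is not met. Restricting infliximab in perforation or sepsis implies that it may be used otherwise. The step, grade and antibody action attached to infliximab cannot be read, because the figure is not shown.
8. *How would the SAP count such a subject?* Section 6.4 would tabulate the drug if it is on the list of immune-modulating medications still to be identified. Table 16 would carry it into the summaries of events of special interest leading to such medication, including recurrence after rechallenge. Section 9 could also count it as a deviation, depending on the Protocol Deviation Management Plan, which is a separate document.

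**The case against.** The strongest answer is that the conflict is narrow and largely resolves itself. Table 6-3 is suggested guidance, most subjects with AST/ALT above 5 x ULN are expected to stop permanently, and resumption in the rest needs Medical Monitor approval. Once both antibodies are permanently stopped, Section 7.2 permits the drug. A specific toxicity algorithm might also be taken to override a general prohibition. On the analysis side, the SAP plainly anticipates immune-modulating treatment, and a deviation flag removes nobody from the ITT, PITT or Safety populations.

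Much of this stands, and it limits the point. A reader might infer that the protocol requires a prohibited drug. It does not: the table is suggested, although Section 6.6 says investigators should follow it. A reader might also infer that giving mycophenolate automatically generates an important deviation. The documents do not show that: the code in SAP Section 9 is only an example, and classification rests with a plan that is not available here.

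It does not remove the inconsistency. The table itself provides for delayed subjects and for resumption, its note does not cover entry on bilirubin alone, and no text gives the algorithm precedence over the prohibition. Medical Monitor approval governs resuming study therapy; it is not stated to waive Section 7.2.

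**Conclusion.** The protocol contradicts itself for a defined group: subjects in the Table 6-3 row for AST/ALT above 5 x ULN or bilirubin above 3 x ULN whose liver tests have not improved, or have worsened or rebounded, and in whom at least one antibody is delayed rather than permanently stopped. A similar gap for infliximab in GI events is likely but not demonstrated, because the algorithm figure is missing from the text reviewed.

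The number of subjects affected cannot be estimated from the documents. A reader might reach for the preliminary triplet data in Protocol Section 1.6, where ALT increased was reported in 10 of 44 subjects (10/44 = 23%). That count is given without grade and says nothing about failure to improve on steroids or about antibody delay, so it does not measure the affected group. Nor do the documents support a claim that the problem falls mainly on the triplet arm. Those data have no nivolumab plus ipilimumab comparison, and Section 6.6.1 attributes liver enzyme and bilirubin elevations to all three drugs.

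The consequences are conflicting instructions to sites during a serious toxicity, and possible double counting of the same treatment as planned management and as a deviation. Sample size, power, type I error and the analysis populations are not affected. This remains worth correcting because two stated rules cannot both be followed and the correction is small.

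**What to change.** The sponsor should reconcile Protocol Sections 7.1 and 7.2, Table 6-3 and Appendix E. A single rule should say whether non-steroid immunosuppressants given under the protocol's own algorithms are permitted while an antibody is only delayed, and each of these places should point to it. Which way the rule goes is a clinical decision for the sponsor.

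The Protocol Deviation Management Plan should then classify algorithm-directed use one way, in line with that rule, so that the SAP Section 6.4 and Section 9 summaries do not give conflicting accounts of the same treatment.

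The cost is about one sentence in Sections 7.1 and 7.2, matching cross-references in Table 6-3 and Appendix E, and one line in the deviation plan. No new procedure, data collection or analysis is needed.
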